9.3. Baseline Visit

At the baseline visit, participants will undergo a comprehensive set of initial assessments. These include:

- Standard medical assessment: with the same evaluations as in the screening visit (except neurological examination).
- Participants will be evaluated for their cognitive status using MOCA
- Pregnancy test if applicable
- Adverse events evaluation
- Venepuncture for blood analysis
- Administration of cognitive tests FLAME Memory Composite
- The study drug will be dispensed to the participant

9.4. Week 2 visit (+/- 3 days)

- **Standard medical assesment:** with the same evaluations as in the baseline visit.
- The study drug will be dispensed to the participant
- Adverse events evaluation
- Venepuncture for blood analysis
- Returned bottles and tablets/capsules counted and recorded for compliance.

9.5. Week 4 visit

- **Standard medical assesment:** with the same evaluations as in the baseline visit.
- Modified C-SSRS
- Pregnancy test if applicable
- The study drug will be dispensed to the participant
- Adverse events evaluation
- Venepuncture for blood analysis
- Returned bottles and tablets/capsules counted and recorded for compliance

9.6. Week 6 visit

- **Standard medical assesment:** with the same evaluations as in the baseline visit.
- The study drug will be dispensed to the participant
- Adverse events evaluation
- Venepuncture for blood analysis
- Returned bottles and tablets/capsules counted and recorded for compliance

9.7. Week 8 visit

- **Standard medical assesment:** with the same evaluations as in the baseline visit.
- Modified C-SSRS
- Pregnancy test if applicable
- Adverse events evaluation
- Venepuncture for blood analysis
- Administration of cognitive tests FLAME Memory Composite
- Lumbar puncture for CSF sampling for biomarker analysis (optional)
- Returned bottles and tablets/capsules counted and recorded for compliance.
- .

9.8. Safety Follow-Up Visit

The safety follow-up visit will occur within 4 weeks after the completion of the dosing period. This visit includes:

- **Standard medical assessment:** with the same evaluations as in screening visit.

- Modified C-SSRS (The C-SSRS will only be conducted at the follow-up/ET visit, if the patient experienced suicidal thoughts during the study treatment period.)
- Safety blood tests

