1.3. Schedule of Activities (SoA)**Table 1. Schedule of Activities**

	Screening (within 28 days before baseline)	Treatment Period					Safety Follow-up ¹ /EOS (within 28 days after last visit)
		Baseline	W2	W4	W6	W8	
Days \pm Visit window	-28 to 0	0	(14\pm 3)	(28\pm 3)	(42\pm 3)	(56\pm 3)	(56\pm 28)
Informed consent	X						
Demographics	X						
Medical history ²	X						
Concomitant medications	X	X	X	X	X	X	X
Vital signs	X	X	X	X	X	X	X
Physical Exam	X	X	X	X	X	X	X
Neurological Exam	X						X
ECG	X	X	X	X	X	X	X
MMSE	X						
MoCA		X				X	
CDR	X						
MRI ³	X						
Suicidal screening using C-SSRS, modified ⁴	X			X		X	X
Inclusion/Exclusion criteria	X	X					
Randomization		X					
Dispense of IMP ⁵		X	X	X	X		
Adverse events		X	X	X	X	X	
AchE sample collection		X	X	X	X	X	

Dose review (for escalation or de-escalation)			X	X	X		
Exosome Biomarker Collection		X	X	X	X	X	
Blood and CSF-based biomarkers ⁶	X					X ⁷	
PK sample collection			X	X	X	X	
Safety laboratory test ⁸	X		X	X	X	X	X
Urinalysis	X		X	X	X	X	X
FSH test ⁹	X						
Pregnancy test ¹⁰	X		X		X		
FLAME Cognitive battery		X				X	

¹ A safety follow-up visit will be conducted within ~4-weeks after the last study-drug dose for all participants who complete the study or who terminate early.

² Includes prior medication use.

³ Only if no MRI scan available within last 2 years.

⁴ The C-SSRS will only be conducted at the follow-up/EOS visit, if the patient experienced suicidal thoughts after the study treatment period.

⁵ Before any dose escalation. According to tolerability and laboratory tests, the dosage will be reassessed, and participants may need to return to the center for a reduced dose.

⁶ CSF samples will only be collected from patients who specifically consent to CSF sample collection and analysis. If CSF biomarker data are available then there is no need for a new CSF collection at screening

⁷ CSF collection at W8 is voluntary and requires an additional informed consent.

⁸ Renal and liver function will be taken every visit. Full Safety laboratory battery will be taken at screening and safety follow-up.

⁹ Women considered post-menopausal will have an FSH test to confirm their status during the screening period and prior to dosing.

¹⁰ Pregnancy testing is required for all women of childbearing potential within one day prior to receiving the first dose of study drug.

2. Introduction

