9.9. Outcome assessment

Outcome assessments will be conducted at key time points throughout the study, as described in the SoA and in detail in the dedicated SOP. Initial evaluations at the baseline visit include cognitive function tests, vital signs, physical examination, liver function tests, and pharmacokinetic sampling. Follow-up visits at Weeks 2, 4, 6 and 8 will involve ongoing safety and tolerability assessments, vital signs monitoring, liver function tests, additional pharmacokinetic sampling, and cognitive assessment will be completed at baseline and Week 8 to track changes. The final safety follow-up visit will include comprehensive safety evaluations, final vital signs, physical examination, laboratory tests to ensure stability, and final cognitive testing. This approach ensures thorough monitoring and data collection on the efficacy and safety of phenserine compared to donepezil.

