9.17.1. Time Period and Frequency for Collecting AE and SAE Information

All SAEs will be collected from the start of treatment until the last follow-up visit at the timepoints specified in the SoA (Section 1.3).

All AEs will be collected from the start of treatment until the last follow-up visit according to the timepoints specified in the SoA (Section 1.3).

Medical occurrences that begin before the start of study intervention but after obtaining informed consent will be recorded as medical history/current medical conditions, not as AEs.

All SAEs will be recorded and reported to the sponsor immediately and under no circumstance should this exceed 24 hours, as indicated in Appendix 4. The investigator will submit any updated SAE data to the sponsor within 24 hours of it being available.

Investigators are not obligated to actively seek information on AEs or SAEs after conclusion of the study participation. However, if the investigator learns of any SAE, including a death, at any time after a participant has been discharged from the study, and the investigator considers the event to be reasonably related to the study intervention or study participation, the investigator must promptly notify the sponsor.

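### The follow-up C-SSRS has two conflicting triggers, and no adverse-event evaluation is scheduled at the safety follow-up visit

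*Protocol*

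**What the plan says.** **C-SSRS.** Table 1 schedules the modified C-SSRS for everyone at Screening, Week 4 and Week 8, and conditionally at follow-up. Footnote 4 limits the follow-up administration to cases "if the patient experienced suicidal thoughts after the study treatment period". Section 9.8 limits it to cases "if the patient experienced suicidal thoughts during the study treatment period". Both conditions are introduced by the word 'only', and 9.8 applies its condition to the early-termination visit as well.

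**Adverse events.** Section 9.17.1 states: "All AEs will be collected from the start of treatment until the last follow-up visit according to the timepoints specified in the SoA". It says the same of serious events. In Table 1 the adverse-event row is marked at Baseline and Weeks 2, 4, 6 and 8, and the follow-up cell is empty. Sections 9.3 to 9.7 each list "Adverse events evaluation". Section 9.8 does not; it asks for a standard medical assessment "with the same evaluations as in screening visit", the C-SSRS on its condition, and safety bloods. The screening list in 9.1 has no adverse-event item. Section 9.9 adds only a general promise: "The final safety follow-up visit will include comprehensive safety evaluations".

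**Visit limit.** Table 1 footnote 1 has the visit "conducted within ~4-weeks after the last study-drug dose", and 9.8 agrees: "The safety follow-up visit will occur within 4 weeks after the completion of the dosing period". SAP 2.4 uses 28 days after last dose. Sections 4.1, 6.3 and the introduction to Section 9 say one week. Section 4.5 gives one week in its definition of a completer and 28 days in the next sentence.

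**The concern.** C-SSRS scores and adverse-event frequencies are both named components of the key secondary safety endpoint in Protocol Section 3. A visit held after drug is stopped exists to find events that persist or begin off treatment. If sites work from different triggers, whether a participant with ideation gets a scored assessment depends on which page the site read. If sites work from Table 1, which Section 9 treats as binding, nothing in the schedule prompts them to ask about adverse events at the last contact. What is at stake is complete and uniform safety ascertainment at one visit. Nothing here bears on the primary biomarker comparison or suggests a difference between arms.

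**Working it through.** No figure in the plan needs reproducing; the check compares the texts.

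**1. C-SSRS trigger.** Classify a participant by ideation during treatment and ideation after treatment.

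| During | After | Footnote 4 | Section 9.8 | Both conditions required | During or after |
|---|---|---|---|---|---|
| no | no | no test | no test | no test | no test |
| yes | no | no test | test | no test | test |
| no | yes | test | no test | no test | test |
| yes | yes | test | test | test | test |

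The two rules disagree on 2 of the 4 patterns. Among the 3 patterns with any ideation, each rule alone tests 2 and misses 1. Treating both as necessary conditions tests 1. A during-or-after rule tests all 3.

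The missed patterns differ in consequence. For someone who attends Week 8, ideation during treatment has already met a scheduled C-SSRS, so footnote 4 costs little. Ideation that first appears off drug has no other scheduled C-SSRS, and 9.8 would miss it. For someone who leaves the study before Week 4, the last unconditional C-SSRS was at Screening; for someone who leaves between Weeks 4 and 8, it was at Week 4. For these participants either missed pattern matters. Section 7 asks for all endpoint assessments at drop-out, which would include the C-SSRS, but the restriction in 9.8 expressly covers the early-termination visit. The two provisions therefore conflict, and neither settles the other.

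**2. Adverse events.** Table 1 has 5 marks (Baseline, Weeks 2, 4, 6, 8) and 0 at follow-up. The blank does not look like an extraction fault: vital signs, physical examination, ECG and concomitant medications all carry a mark in that column. Section 9.17.1 sets the end of collection at the last follow-up visit and hands the timing to a schedule that has no entry there, so it contradicts itself.

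Other text shows the intention. Section 9.17.2 follows events until they resolve or are judged chronic or stable. Section 9.17.3 requires active follow-up at later visits once an event has been reported. Appendix 3 has unsolicited events that were not already reported gathered by interview and record review at the next visit, which after Week 8 is the safety follow-up.

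**3. Visit limit.** The limits are 7 and 28 days, so 28 − 7 = 21 days (days 8 to 28) are allowed by some sections and late under others. A visit by day 7 satisfies every upper limit. Because SAP 2.4 fixes 28 days, no analysis set or analysis window changes. What can change is labelling: whether a visit on days 8 to 28 satisfies the completer definition in 4.5, and whether it counts as a minor deviation under SAP 3.4.2.

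**The case against.** The strongest reply is that these are drafting slips with safeguards around them. Much of that stands.

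- Section 9.16 monitors all participants for ideation, with a risk assessment if suicidal behaviour is seen and immediate reporting by the informant. The gap is in the scored instrument at one visit.
- SAP 8.1 and the SAP outcome table do not list C-SSRS scores, so no specified summary uses a follow-up score. They remain part of the endpoint because SAP 2.3 takes its endpoints from Protocol Section 3 and Table 2.
- Section 9.9 refers to a dedicated SOP, which may already give sites one working rule. It is not among the documents.

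Four stronger readings are tempting, and the documents do not support them.

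- A reader might infer that adverse events go uncollected once drug is stopped. Sections 9.17.2, 9.17.3 and Appendix 3 say otherwise.
- A reader might infer that a site cannot comply with both C-SSRS rules. If each 'only' is read as a necessary condition, it can, by testing only participants with ideation in both periods. That is compliant but gives the poorest coverage.
- A reader might take the 56 ± 28 entry in Table 1 to allow the visit from Day 28, during treatment. The heading of the same column, within 28 days after the last visit, rules this out.
- A reader might think that the disputed visit limit alters the analysis. SAP 2.4 settles that it does not.

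What the reply does not remove is that the two triggers select different participants and that the schedule omits an evaluation which 9.17.1 requires.

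**Conclusion.** The point holds for the C-SSRS trigger and for the adverse-event entry, and both should be corrected. Under either trigger as written, 1 of the 3 ideation patterns gets no scored C-SSRS at follow-up, with the greatest exposure among early terminators. The number of participants affected cannot be given, because the documents state no expected frequency of ideation; the trial plans 16. The adverse-event point is a contradiction between 9.17.1 and the schedule (5 marked visits, none at follow-up) in a protocol that otherwise intends capture. The visit limit is a minor matter of consistency. The conclusion assumes that the empty cell in Table 1 is as printed and that no SOP outside these documents already resolves the wording.

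**What to change.** 1. In Table 1 footnote 4 and in 9.8, use one trigger: suicidal thoughts during or after the study treatment period.
2. In Table 1, mark adverse events in the follow-up column, and add to 9.8 the same adverse-event item that 9.3 to 9.7 carry.
3. As a minor correction, state 28 days after last dose, as in SAP 2.4, as the follow-up limit in 1.3, 4.1, 4.5, 6.3, 9 and 9.8, and replace 56 ± 28 with an entry that matches its column heading. If the early-termination visit in 4.1 and 9 keeps its own one-week limit, say that it is a separate visit.

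The cost is protocol wording; SAP 2.4 needs no change. Under 11.1.1, ethics approval is needed before design changes are implemented, and health-authority approval if the amendment is substantial, so this can travel with the next planned amendment. The wider trigger adds a questionnaire only for participants with ideation. The documents do not give enrolment status; if dosing is already complete, the sponsor should instead record which C-SSRS rule sites applied and which adverse-event period is reported.

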9.9. Outcome assessment

Outcome assessments will be conducted at key time points throughout the study, as described in the SoA and in detail in the dedicated SOP. Initial evaluations at the baseline visit include cognitive function tests, vital signs, physical examination, liver function tests, and pharmacokinetic sampling. Follow-up visits at Weeks 2, 4, 6 and 8 will involve ongoing safety and tolerability assessments, vital signs monitoring, liver function tests, additional pharmacokinetic sampling, and cognitive assessment will be completed at baseline and Week 8 to track changes. The final safety follow-up visit will include comprehensive safety evaluations, final vital signs, physical examination, laboratory tests to ensure stability, and final cognitive testing. This approach ensures thorough monitoring and data collection on the efficacy and safety of phenserine compared to donepezil.

9.10. Efficacy Assessments

Planned timepoints for all efficacy assessments are provided in the SoA.

9.11. Safety Assessments

Planned timepoints for all safety assessments are provided in the SoA.

9.12. Computerized cognitive testing

FLAME computer-based cognitive testing is performed on a highly standardized digital portal, with no input from staff other than setting it up.

We will ensure that all investigators participating in data collection are appropriately trained in administering the FLAME computerized cognitive battery and have a comprehensive understanding of the test's instructions, scoring criteria, and potential challenges in participants. It is important to familiarize investigators with the study's objectives, ethical guidelines, and the importance of data accuracy.

Assessments are conducted in a quiet and well-lit room within the memory clinic to minimize distractions and ensure participant comfort.

Standardized Instructions:

Begin by providing standardized instructions to participants, explaining the purpose of the assessment and what to expect during the testing.

FLAME Memory Composite:

Administer the FLAME Cognitive Battery following the specific test sequence recommended by the manufacturer.

Ensure that each subtest is administered consistently across all participants, adhering to the standardized instructions provided by the battery.

Monitor participants' responses and progress through the battery, providing necessary guidance or clarification when required.

Data Recording: Record participants' responses and performance with the FLAME computerized cognitive battery accurately, ensuring that all data points are collected in real-time.

Table 5. Tasks Included in Memory Composite score, the Primary outcome:

Task	Timings (minutes)	Description
Picture Recognition (Visual episodic memory)	3.5	At the start of the battery 20 pictures are presented for an equal time on screen. At the end of the battery the original pictures plus the 20 very similar distractor pictures are presented one at a time in a counterbalanced order. For each picture the subject has to indicate whether or not it was the precise picture shown earlier, as quickly and accurately as possible. Each picture remains on the screen until a response is made. The accuracy and speed of each response is recorded.
Self-ordered search (working memory)	5 Minutes Average (however, this task is performance driven so can be as short as 1.5 minutes)	Participants search a series of on-screen boxes to find a hidden symbol. Once found, participants search for the symbol again, remembering that the symbol will never be hidden in the same box twice. The symbol is hidden in every box once per level. After successfully completing a level, a new level opens with more boxes to search than the previous level. The outcome measure is the average number of boxes in the successfully completed trials. Participants are allowed three errors before the test terminates. This task measures working memory
Paired Associate Learning (working memory)	3 Average (however, this task is performance driven so can be as short as 1.5 minutes)	Participants are shown objects, one per “window” in a grid. Then they see the series of objects, one at a time in a random order, and select the correct “window” where the object had previously appeared. This version uses a ratchet- style approach, each successful trial is followed by one with more objects to recall and each unsuccessful trial is followed by the same number of objects as in the unsuccessful attempt. The outcome measure is the average number of correct object-place associations (“paired associates”) in the trials that were successfully completed. Participants are allowed three errors before the test terminates. This task measures working memory and learning/episodic memory.
Digit Span (numerical working memory)	3 Minutes Average (however, this task is performance driven so can be as short as 1.5 minutes)	A series of numbers is shown to the participant who then enters the numbers in the same sequence as they appeared using a number keypad. The test uses a ratchet-style approach in which each successful trial is followed by a new sequence that is one digit longer than the last and each unsuccessful trial is followed by a new sequence that has the same number of digits as the unsuccessful trial. This allows an accurate estimate of digit span to be made quickly. The outcome measure is the average number of digits in all successfully completed trials. Participants are allowed three errors before the test terminates.
Total	13	

Table 6. Digital cognitive tests included in the secondary cognitive outcome

Task	Timings (minutes)	Description
Simple Reaction Time	2	The subject is required to respond as quickly as possible when a stimulus is presented in the center of the screen. The subject is informed that the stimuli will be presented one at a time and that they will remain there until a response is made. The speed of each response is recorded.
Digit Vigilance	3	A target digit from 1 to 9 is randomly selected and constantly displayed to the right-hand side of the screen. Digits are then presented one at a time in the center of the screen. The subject is required to respond as quickly as possible every time a digit matches the target digit. Correct detections, the speed of the detections and responses made in error (false alarms) are recorded.
Choice Reaction Time	2	The two possible stimuli in this task that appear on screen. Equal amounts of each stimuli type will be displayed. The subject is required to respond with the correct response key as quickly as possible every time the stimuli appear on screen. The accuracy and speed of each response is recorded.
Delayed Visual Recognition (Picture Recognition)	3.5	At the start of the battery 20 pictures are presented for an equal time on screen. At the end of the battery the original pictures plus the 20 very similar distractor pictures are presented one at a time in a counterbalanced order. For each picture the subject has to indicate whether or not it was the precise picture shown earlier, as quickly and accurately as possible. Each picture remains on the screen until a response is made. The accuracy and speed of each response is recorded.
Verbal Reasoning	3	A sentence is displayed at the bottom of the screen whilst a square and a circle are displayed above. The participant needs to respond true or false as to whether the sentence correctly describes the configuration of the circle and square. Participants are given three minutes to solve as many problems as they can. The task measures verbal reasoning.
Total	15	

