6.4. Blinding

The study intervention will be open label. No blinding will be performed. Participants and site staff will, however, will be blinded to the results of the exosome and blood/CSF biomarker evaluations until the study is completed.

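### Protocol 9.12 says FLAME needs no staff input beyond set-up, then has staff who know the arm give guidance during the battery; it also lists Picture Recognition in two tables with no scoring rule

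*Protocol*

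**What the plan says.** **Staff role.** Protocol 9.12 opens by saying that FLAME is "performed on a highly standardized digital portal, with no input from staff other than setting it up". Under the FLAME Memory Composite sub-heading it then has staff watch how the participant responds and advances through the tests, "providing necessary guidance or clarification when required". The line just before that instruction is a safeguard: "Ensure that each subtest is administered consistently across all participants, adhering to the standardized instructions provided by the battery". The section also asks for trained administrators, a fixed test order and a standard introduction before testing.

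**Masking.** Protocol 6.4 states: "The study intervention will be open label. No blinding will be performed". Section 6.3.1 confirms that participants and site staff know the assignment. What is masked is the exosome and blood/CSF biomarker results; cognitive testing is not included. FLAME is given at baseline and Week 8 (Table 1), and section 9.2 allows randomization before the baseline visit as well as during it.

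**Picture Recognition.** The first row of Table 5, the memory composite, begins "Picture Recognition (Visual episodic memory". A row of Table 6, the secondary cognitive outcome, begins "Delayed Visual Recognition (Picture Recognition". Both rows carry 3.5 minutes and the same description.

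**Status of FLAME.** It is exploratory (Protocol section 3 and 3.2.3; SAP 4.5). SAP 9.2 plans change from baseline in FLAME domain scores and individual change plots. Neither document says which task feeds which domain.

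**The concern.** In an open-label trial, a self-running computerized battery is a natural protection against the tester's expectations, and the opening of 9.12 claims that protection. The later instruction withdraws it: staff who know the arm may watch responses and help as the participant works. If help is given during scored trials, and more readily in one arm, part of the FLAME difference reflects the testing and not the drug.

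FLAME is exploratory, but it has a use. Protocol 2.3.3 includes the cognitive assessments among the results that will guide dose and outcome choices for Phase 2. Protocol 3.2.3 sets FLAME changes beside exosome changes, by arm and for individual participants. With 4 donepezil participants, one unusual session carries weight.

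The second matter is one of definition. The same picture-recognition data could feed two reported cognitive outcomes, because nothing in either document says where the task is scored.

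**Working it through.** Neither document gives a figure for staff influence on FLAME, so there is none to reproduce. The check is mainly a comparison of text, with a small illustration of scale.

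**1. Can both sentences in 9.12 hold?** The first limits staff to set-up. The second has them act as the participant moves through the battery. Instructions given beforehand are covered separately in the same section, so the second sentence appears to reach further than that. It does not say whether help may be given while a trial is being scored, and 9.12 gives no script, limit or log for it.

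**2. Can help differ by arm?** Staff know the arm at Week 8 (6.3.1, 6.4). Because 9.2 lets randomization come before the baseline visit, they may know it at the baseline FLAME too. No tester unaware of the arm is named. FLAME is analysed as change from baseline, so unequal help that was the same at both visits would cancel. Unequal help at one visit, or of different size at the two visits, would not. The direction cannot be predicted.

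**3. Scale, for illustration only.** Arm sizes are 12 and 4 (SAP section 3). Assume that help raises one participant's change score by 1 SD; this is not a figure from the documents.

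- Shift in an arm mean = lift / arm size
- Donepezil: 1 / 4 = 0.25 SD
- Phenserine: 1 / 12 = 0.08 SD

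For context, the half-width of a two-sample 95% confidence interval at 12 versus 4, in SD units, is t(0.975, 14 df) × √(1/12 + 1/4) = 2.145 × 0.577 = 1.24. A 0.25 SD shift is 0.25 / 1.24, about 20% of that. It is small beside the sampling uncertainty, and for the same reason the data could neither reveal it nor rule it out.

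**4. Do the table timings show where Picture Recognition belongs?**

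| | Sum of rows (min) | Stated total (min) |
|---|---|---|
| Table 5 | 3.5 + 5 + 3 + 3 = 14.5 | 13 |
| Table 6 | 2 + 3 + 2 + 3.5 + 3 = 13.5 | 15 |
| Both | 28 | 28 |

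Neither stated total matches its own rows. The combined totals agree only with the task listed in both tables; counted once, the rows give 28 − 3.5 = 24.5. Timing is not a scoring rule, so this does not show whether the task enters one score or two.

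**The case against.** **Safeguards exist.** Consistent administration under the battery's own instructions is required in the line before the disputed one, and testers are trained. Guidance may mean no more than explaining a task, which is reasonable in people with early or mild AD. Protocol 9.9 places the detail of outcome assessments in an SOP that is not available here, so a script or limit may exist there. This stands in part: it narrows the risk and rules out saying that steering will occur. It does not reconcile two sentences in the protocol itself.

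**FLAME is exploratory.** It is summarised descriptively, with no formal testing (SAP 2.3.1 and section 5), and MoCA is reported beside it. This stands, and it keeps the point minor.

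**Scripting staff does not make the test blind.** Participants know their arm, which can affect effort. This stands too; the fix closes one route only.

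**Stronger readings.** Three are tempting, and the documents do not support them.

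- A reader might infer that Picture Recognition is counted twice, or that a memory effect leaks into a non-memory outcome. No score is shown to include the task twice. Table 6 is not described as non-memory, no composite is defined from it, and the SAP analyses domain scores. If the task feeds only the memory domain, it counts once.
- A reader might quantify the overlap as a correlation between the two tables' scores. That would need a Table 6 score that is not defined, and assumed correlations between tasks.
- A reader might set 0.25 SD against the effect size of 0.3–0.4 quoted in Protocol 2.3.1. That comes from an earlier trial with a placebo group. Here donepezil is included to control for cholinesterase inhibition (2.1), so it is not the expected contrast.

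**Conclusion.** The point holds as a minor one. Protocol 9.12 contradicts itself on the staff role, and because staff know the arm, the text leaves an avoidable route by which help could differ between arms and bias the FLAME contrast. Neither the size nor the direction of any bias can be derived from the documents. The 0.25 SD figure rests on an assumed 1 SD lift in one of 4 donepezil participants, not offset at the other visit, and serves only to show how much one session weighs. Standardized administration reduces the risk, and participants' knowledge of their arm would remain after any change in staff conduct.

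On Picture Recognition, what is supported is a duplicate listing together with no rule assigning tasks to domains.

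**What to change.** **Protocol 9.12 and the SOP.** Reconcile the two sentences so that staff give only scripted instructions, practice and clarification, all before scored trials begin. Log any unavoidable interruption, with the subtest and the reason.

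**SAP 9.2.** Keep every session in the main FLAME summary. Repeat the analysis without the logged sessions as a sensitivity analysis only: it excludes participants on something that happens after randomization and may remove the more impaired. Note when interpreting FLAME that participants knew their arm.

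**Picture Recognition.** State in the SAP that it is scored once, in the memory domain, and give the task-to-domain assignment for the rest of the battery. Bring Tables 5 and 6 into line, including their time totals and the Table 5 title, which still calls the memory composite the primary outcome although the primary is exosome biomarkers (3.2.1).

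**Cost.** Protocol, SOP and SAP wording. The real downside is an occasional invalid subtest when a participant misunderstands a task and cannot be helped. SAP section 6 uses observed data without imputation, so one loss in the donepezil arm is 1/4 = 25% of the comparator for that score. Practice items before scoring should make this less frequent.
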